## **5. SUBJECT RECRUITMENT METHODS AND PRIVACY**

Subjects are recruited primarily through formal advertisement (i.e., regular newspaper advertisements placed generally in free newspapers), local flyers posted in public areas (e.g., bars, restaurants, stores) and by word-of-mouth. These advertisements are approved under our screening protocol (IRB # 03-0509). Subjects will make initial contact by phone with one of our recruiters who have completed the research training and HIPAA compliance web-based teaching models. If the

subject self-discloses information that would make him/her potentially eligible for the study, they will be invited to come in for a screening appointment. Screening is completed by one of our research assistants at the UK Laboratory of Human Behavioral Pharmacology (LHBP). Study investigators may interact with subjects in this setting and appropriate cautions are in place to ensure privacy during the intake process.

## 6. INFORMED CONSENT PROCESS

All potential subjects that are identified using the subject recruitment methods noted above will provide informed consent prior to participating in the protocol. Subjects that meet the eligibility criteria noted above will come to the LHBP and will undergo a field sobriety test and provide an expired air sample that will be tested for the presence of alcohol. If the subject passes the field sobriety test (walk and turn, one-leg balance [timed], finger-to-nose and backwards-counting tasks) and the expired air sample is negative, he or she will then be given a copy of the approved informed consent document to read and sign. After reading the consent document, the PI or one of the Co-Is on this protocol will address any questions the subject may have in order to assess the subject's understanding of the protocol. After this, the subject will receive a copy of the informed consent document and will sign a form indicating that they have received a copy of the form they read and signed.

## 7. RESEARCH PROCEDURES

*General Procedures.* Subjects that meet the inclusion criteria will participate as inpatients at the University of Kentucky CCTS Research Inpatient Unit (CRIU). Subjects will be discharged upon completion of the entire protocol.

This experiment will require each subject to participate for approximately five weeks. Experimental sessions will be conducted as outlined in Table 1 below. We would like to note that COC doses will both be given in random order, whereas order of PHEN dosing will be counterbalanced across subjects. We would also like to note that subjects may be maintained on a given PHEN condition for more than 11 days prior to session to avoid testing COC doses on weekends.

Day	Table 1. Experimental Procedures
1	Admission to the CRIU.
2	Practice Session.
3-17	Placebo maintenance. Placebo administered twice daily (0700 and 1900 hours).
14-17	Experimental Sessions. Reinforcing effects of intranasal COC (0 [placebo], 20, 40 and 80 mg) determined using progressive-ratio procedure.
18-32	PHEN maintenance. Administered in divided doses (0700 and 1900 hours). Subjects receive 35 mg twice daily for two days, then 70 mg twice daily for two days, then 105 mg twice daily for remainder of maintenance period.
29-32	Experimental Sessions. Reinforcing effects of intranasal COC (0 [placebo], 20, 40 and 80 mg) determined using progressive-ratio procedure.
33	Discharge

During their participation in the research protocol, subjects will not be allowed to leave the CRIU, nor will visitors be allowed, with the exception that subjects can leave for walks under clinical supervision and if approved by physicians. Research subjects will be allowed to make local telephone calls. After completing the research protocol, interested subjects will be offered a referral to an appropriate drug abuse treatment program.

All subjects will provide urine and expired air samples before and periodically during study participation. The presence of non-nicotine drugs of abuse or alcohol not administered experimentally in the research protocol will result in immediate termination from the research study.

This experiment will consist of 1 practice session and 8 experimental sessions conducted according to the timeline in Table 1 (see above). After admission, subjects will be allowed to acclimate to the CRIU for two days before beginning the study. During this time, subjects will be maintained on a caffeine-free diet, receive instructions concerning the details of the daily research procedures and general rules of the inpatient research unit and complete a "practice" session to familiarize them with the experimental routine and tasks.

Each day after the practice session, subjects will be awakened at 0700 hours and will receive maintenance medication. Medications will not be administered if a subject's heart rate is  $\geq 100$  bpm, systolic pressure is  $\geq 150$  mmHg or diastolic pressure is  $\geq 100$  mmHg. In addition, the UKU side effects scale will be completed daily to monitor for the emergence of side effects.

Subjects will then be allowed to eat a standard, fat-free breakfast (cereal with skim milk, 2 pieces of toast with jam or jelly and 8 ounces of fruit juice). Tables 2 and 3 (below) outline the activities of maintenance and experimental sessions. The sampling of each session will begin at 0900 hours and will last approximately 1 hour. Self-administration phases will begin at 1330 hours and will last approximately 2 hours. Experimental measures will be completed as outlined in Tables 2 and 3 below. Medications will not be administered if a subject's heart rate is  $\geq 100$  bpm, systolic pressure is  $\geq 150$  mmHg or diastolic pressure is  $\geq 100$  mmHg or if clinically significant and/or prolonged ECG abnormalities are detected.

Subjects will be excluded from further research participation if at any time during the experimental sessions COC increases heart rate above 130 bpm, systolic pressure above 180 mmHg, diastolic pressure above 120 mmHg or if clinically significant and/or prolonged ECG abnormalities are noted. Subjects will remain seated for the duration of the experimental session. Between the sampling and self-administration phases, subjects will be allowed to eat a standard hospital lunch but will not be allowed to smoke. No experimental activities will be scheduled for the remainder of the day after a self-administration session, but subjects will receive their appropriate maintenance medication at 1900 hours. Subjects will be free to engage in recreational activities (e.g., watch television, read, listen to music, arts and crafts, play video or board games). Research subjects will be required to be in bed with the lights out by 2300 hours.

Time	Table 2-Daily Activities for Maintenance Days
0700	Patient awakened. Vital signs recorded. Medication administered if vitals are within range and no indication of sedation or withdrawal. Subject eats breakfast.
1200	Lunch is served.
1300	UKU completed.
1900	Dinner is served. Vital signs recorded. Medication administered if vitals are within range and no indication of sedation or withdrawal.
2300	Lights out.

Time	Table 3-Daily Activities for Experimental Days
0700	Patient awakened. Vital signs recorded. Medication administered if vitals are within range and no indication of sedation or withdrawal. Subject eats breakfast.
0900	Vital signs recorded. Computerized tasks completed. ECG monitoring begins.
0930	Vital signs recorded. 0 [placebo], 20, 40 or 80 mg intranasal COC administered if vitals are within range. Measures completed 0, 15, 30, 45 and 60 minutes after drug administration.
1030	Sampling phase ends.
1200	Lunch is served.
1300	UKU is completed.
1330	Vital signs recorded. Computerized tasks completed (including progressive-ratio task). ECG

	monitoring begins.
1430	Vital signs recorded. Portion of intranasal dose earned is administered if vitals are within range. Measures completed 0, 15, 30, 45 and 60 minutes after drug administration
1530	Session ends. Remainder of daily activities identical to those listed in Table 2.

All drugs will be administered under double-blind conditions and under medical supervision. Test doses of COC will be 0 (placebo), 20, 40 and 80 mg, administered in random order. These doses were chosen based on prior work and similar doses have safely been administered to human subjects (Oliveto et al., 1995; [name] et al., Ongoing Study; [name] et al., 2008; 2010; 2012a; 2012b; Van Dyke et al., 1978). The maintenance conditions will be placebo and 210 mg PHEN/day (target dose). Subjects will be maintained on these doses for at least seven days before beginning experimental sessions. The dose of PHEN was selected based on results of previous clinical research, as well as a recently completed and ongoing studies in our laboratory showing that this PHEN dose is well tolerated by COC users (Bolin et al., Under Review; [name] et al., Ongoing). Placebo capsules will contain only cornstarch, whereas placebo powder will contain only lactose. Both will be visually identical to the powder and capsules that contain active drug.

**Apparatus.** Behavioral testing will be conducted at the CRIU. Subjects will be tested using an individual Macintosh laptop computer that automates behavioral tasks.

**Modified Progressive-Ratio Procedures.** The reinforcing effects of intranasal COC, alone and during maintenance on PHEN doses will be assessed using a progressive-ratio procedure. The outcome measures for this procedure are the break point (i.e., last ratio completed) and number of drug doses ingested.

Testing of each dose of intranasal COC under the proposed modified progressive-ratio procedure involves two phases: 1) Sampling and 2) Self-Administration.

**Sampling Phase.** Participants will complete a Sampling Phase for each of the active intranasal COC conditions to acquaint them with the drug effects. During each Sampling Phase, participants will receive a single administration of intranasal COC (0 [placebo], 20, 40 or 80 mg). Before each Sampling Phase, participants will be instructed to attend to the effects of the intranasal drug because later that day they will be able to work to receive additional doses of the inhaled drug. Participants will complete the battery of subjective effects questionnaires and performance task 30 minutes before the sampling dose of intranasal COC, immediately following and at 15-min intervals for 60 minutes. Cardiovascular measures will also be recorded at these times.

**Self-Administration Phase.** Four hours after sampling the available COC dose, participants will complete the Self-Administration Phase. During the Self-Administration Phase, participants will be given up to 10 opportunities to earn 1/10 of the dose of COC dose insufflated during the Sampling Phase or \$0.25. Before the Self-Administration Phase, participants will be instructed that the total amount of drug/money earned will be administered after completing the entire progressive-ratio procedure. Participants must choose one of the two options at each of the 10 opportunities. Participants will be able to earn drug doses or money by responding on a computer mouse according to a progressive-ratio schedule. The ratio for the first choice will be 400 clicks. The response requirement will increase by 100 for a selected option (i.e., 500, 600, 700, 800, 900, 1000, 1100, 1200, 1300 responses if the subject exclusively chooses drug or money). We have conducted several experiments in recent years designed to refine human drug self-administration procedures to enhance our ability to determine the initial efficacy of potential pharmacotherapies for stimulant dependence (Sevak et al., 2010; [name] et al., 2011). The results of ongoing experiments that used progressive ratio procedures nearly identical to those proposed in this application suggest that the reinforcing effects of oral and intranasal stimulants are an orderly function of dose (Marks et al., Under Review; Pike et al., 2014; [name] et al., 2012a). Previous studies have also shown that the reinforcing effects of COC are amenable to pharmacological manipulation under a similar arrangement (Greenwald et al., 2010; [name] et al., 2012a).

**Subjective Questionnaires.** A battery of subjective questionnaires will also be used to assess drug effects. These measures have previously been shown to be sensitive to the effects of stimulants ([name] et al., 2009). These experimental measures will be taken on all experimental session days. The measures described below will be recorded as described in the tables above. The subjective effects measures are included in Appendix A.

**Vital Signs.** Heart rate, blood pressure, oral temperature and heart rhythmicity (via ECG) will be recorded using a Dinamap digital monitor (Critikon, Pro 1000, Tampa, FL). These measures will be completed at as described in the tables above. Telemetry-certified nurses will interpret the results of the ECG with instructions to contact Drs. [name] or [name] regarding abnormalities.

**Performance Task.** Psychomotor performance will be assessed at the same time as subjective drug-effects during all sessions with a computerized version of the Digit-Symbol-Substitution Test (DSST) (McLeod et al., 1982). In this procedure, the subject uses a numeric keypad to enter a geometric pattern displayed on a video screen. Subjects will have 90 seconds to enter as many geometric patterns as possible. The dependent measures are the number of geometric patterns the subject attempted to enter and the number of patterns entered correctly. This task will be completed immediately following the subjective questionnaires.

**Drug Dose and Administration.** All drugs will be administered under double-blind conditions and under medical supervision. COC doses will be given in random order. PHEN doses will be given in counterbalanced order across subjects. Doses of COC HCl will be prepared by weighing out the appropriate amount of powdered COC. The powder will then be mixed with lactose monohydrate powder, N.F. to make a total of 100 mg powder. Placebo will be prepared in an identical fashion, but will contain only lactose monohydrate powder. Doses of COC will be prepared individually for each subject. Doses of 0 [placebo], 20, 40 and 80 mg intranasal COC will be placed into individual glass vials labeled for each subject for each sampling session. Doses of PHEN (0, 35, 70 and 105 mg, administered two times daily) will be prepared by over-encapsulating commercially available tablets in a size 0 capsule. The capsule will then be loose filled with cornstarch. Placebo capsules will be prepared in an identical fashion, but will contain only cornstarch.

**Data Analysis.** Data will be analyzed as raw scores. Statistical significance refers to  $p \leq 0.05$ .

Progressive-ratio data (i.e., break point, number of COC doses earned) will be analyzed with two-factor mixed-model ANOVA with COC (within-subject variable; 0 [placebo], 20, 40 and 80 mg), and PHEN (within-subject variable; 0 and 210 mg/day) as the factors. A significant attenuation (i.e., rightward shift in the dose response) of the effects of COC will be inferred if the main effect of PHEN or the interaction of COC and PHEN attains statistical significance in the ANOVA. If the COC-PHEN interaction attains statistical significance, the mean square error term will be used to conduct Tukey's HSD *post-hoc* test to make appropriate pair-wise comparisons between means. Peak-effect and AUC data for the cardiovascular, performance and subjective effects measures obtained during the sampling phase will be analyzed in a similar fashion. Cardiovascular, performance and subjective effects data from the self-administration phase will not be analyzed because participants will likely ingest varying amounts of COC making these data difficult to interpret.

The primary outcome measures for this study are the break point and number of COC doses earned on the progressive-ratio procedure in subjects maintained on active PHEN or placebo. Considering the complete within-subject design, number of dose levels of each drug (i.e., two PHEN conditions and four doses of intranasal COC) enrolling 36 subjects will provide adequate power to detect an effect size ( $d$ ) of at least 0.44 for attenuation of the reinforcing effects of COC as a function of maintenance on PHEN and placebo ( $\text{power} = 0.80$ ,  $\alpha = 0.05$ , G\*Power). We used the results of a previous study conducted in our laboratory to determine an appropriate sample size for the present experiment ([name] et al., 2010). That study demonstrated that d-amphetamine maintenance decreased the reinforcing effects of COC with an estimated effect size ( $d$ ) of approximately 0.46.

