## **15. PAYMENT**

Subjects will be paid \$40 for each day they reside on the CRIU and will receive a \$40 completion allowance for these days if they complete the entire experiment. Subjects can also earn an additional \$2.50 during each experimental session depending on how they distribute choices for drug and money. Any money earned in experimental sessions will be added to their overall payment. The amount earned by the subject will be disbursed to them upon completion of the study. Payments will be disbursed in amounts up to \$500 dollars and will be given once per week following discharge until the subject is paid in full. When subjects return on a weekly basis to receive their payments, we will survey them regarding

their drug use since being discharged from the study. A subject can earn approximately \$2660 for participating in this study.

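### The choice task promises drug and money after the procedure, but section 15 pays the money only from discharge, at a delay that differs between the two blocks

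*Combined protocol and SAP*

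**What the plan says.** Section 7, Self-Administration Phase, gives subjects "up to 10 opportunities to earn 1/10 of the dose of COC dose insufflated during the Sampling Phase or \$0.25", with one option to be chosen each time. Beforehand they are "instructed that the total amount of drug/money earned will be administered after completing the entire progressive-ratio procedure". The wording makes no distinction between drug and money.

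Table 3 schedules the progressive-ratio task at 1330. At 1430 it states: "Portion of intranasal dose earned is administered if vitals are within range". No row of Table 3 hands over money.

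Section 15 treats the money differently. It says: "Subjects can also earn an additional \$2.50 during each experimental session depending on how they distribute choices for drug and money". It continues: "Any money earned in experimental sessions will be added to their overall payment". On timing it says: "The amount earned by the subject will be disbursed to them upon completion of the study". Payments are capped at $500 each and "will be given once per week following discharge until the subject is paid in full".

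Table 1 places the experimental sessions on days 14-17 and 29-32 and discharge on day 33. The Data Analysis part of section 7 names break point and number of COC doses earned as the primary outcomes, analysed by an ANOVA with COC dose and PHEN condition as its two factors. PHEN order is counterbalanced across subjects.

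**The concern.** Both primary outcomes are produced by repeated choices between a fraction of a cocaine dose and $0.25, so the value of the money option is part of the measuring instrument. Two things follow from reading the sections together. First, one option is delivered as the instruction says and the other is not. Second, the wait for money is more than two weeks in the first block and a few days in the second if it is paid at discharge, so the two halves of the crossover do not offer quite the same alternative. If subjects weigh that wait, drug choice could shift between blocks for a reason unrelated to PHEN. The analysis has no term to absorb such a shift.

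**Working it through.** **1. Is the session money inside the post-discharge payment?** The inputs are all in the protocol: $40 per inpatient day, a $40 completion allowance for these days, 8 sessions at up to $2.50, and 33 days in Table 1.

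33 x $40 + 33 x $40 + 8 x $2.50 = 1320 + 1320 + 20 = $2660.

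This matches section 15's stated total exactly. Counting 32 days gives $2580, and a single $40 allowance gives $1380. The stated total therefore includes the $20 of choice money, in line with section 15's text.

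**2. Minimum delay to money** (day 33 minus session day):

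| Block | Session days | Delay, days | Mean, days |
|---|---|---|---|
| 1 | 14, 15, 16, 17 | 19, 18, 17, 16 | 17.5 |
| 2 | 29, 30, 31, 32 | 4, 3, 2, 1 | 2.5 |

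The block means differ by 17.5 - 2.5 = 15 days. Drug is given about one hour after the task starts (1330 to 1430), if vital signs allow. Section 7 lets the maintenance period be lengthened to avoid weekend testing, so individual delays can move by some days.

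**3. Longer delay if a later instalment carries the money.** 2660 / 500 = 5.32, so six payments at the cap. Five payments cover $2500 of the $2640 that is not choice money, so choice money counted last falls in the sixth. That payment comes 5 x 7 = 35 days after the first.

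- First payment at discharge: 51-54 days for block 1 and 36-39 for block 2.
- First payment a week after discharge: 58-61 and 43-46 days.

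The documents do not say which instalment carries the choice money or exactly when the first is paid.

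**4. Illustration only: what the delay could do to the value of $0.25.** Hyperbolic discounting, V = 0.25 / (1 + kD), is an assumption, and so is every k (per day) below. Neither is in the documents. The ratio of block 1 value to block 2 value is (1 + k x D2) / (1 + k x D1).

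| k | Paid on day 33 (17.5 v 2.5 days) | Paid in sixth instalment, first at discharge (52.5 v 37.5 days) |
|---|---|---|
| 0.01 | 1.025/1.175 = 87% | 1.375/1.525 = 90% |
| 0.05 | 1.125/1.875 = 60% | 2.875/3.625 = 79% |
| 0.10 | 1.250/2.750 = 45% | 4.750/6.250 = 76% |

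The result depends heavily on both unknowns. It concerns the value of the money, not drug choice.

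**5. Effect on the PHEN contrast.** Suppose the block difference shifts the outcome by p from block 1 to block 2. A subject who takes PHEN second has a PHEN-placebo difference shifted by +p; one who takes it first has it shifted by -p. With equal numbers in the two orders the mean shift is (+p - p)/2 = 0. The shifts still add p squared to the variance of the individual differences when no period term is fitted. The documents give no choice data from which to estimate p.

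**The case against.** **The instruction can be read more loosely.** It says after the procedure, not right after. Its main purpose may be to tell subjects that they receive one total at the end rather than a delivery after each choice. Crediting the money to an account that afternoon would fit both sections. No section says this is what happens, however, and the same verb covers drug given that day. The consent pages are not in the available text, so what subjects know about payment timing cannot be seen. A reader might infer that subjects are deceived; the documents do not establish that.

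**The two harms do not both apply in full.** Subjects who believe money comes that day do not discount it by weeks, and subjects who know it comes after discharge are not misled. This stands, and it is one reason why the effect cannot be sized.

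**The treatment comparison is protected.** A reader might infer that delayed money biases the PHEN effect. It does not bias the average contrast: payment rules are identical under PHEN and placebo, and order is counterbalanced. All four COC doses fall within one block in random order, so dose comparisons within a block differ by at most 3 days of delay.

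**Loss of sensitivity is not shown.** A reader might also infer that delayed money leaves less room to see PHEN lower cocaine choice. Higher baseline drug choice leaves more room to fall, unless choice is so dominant that PHEN cannot move it, and no data here show that. The schedule works against exclusive choice: ten drug choices cost 8,500 clicks, while a five-five split costs 2 x (400 + 500 + 600 + 700 + 800) = 6,000. Section 7 also reports orderly dose functions with nearly identical procedures and sensitivity to medication under a similar arrangement. It does not say how money was paid in those studies.

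**Cash may not remove the whole delay.** Subjects are confined to the unit apart from supervised walks, and the documents show no way to spend the money there. This limits the benefit of same-day payment, but not its agreement with the instruction.

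**Conclusion.** Section 7 and section 15 disagree on when choice money is delivered, in the task that generates both primary outcomes. The size that can be stated is the delay: under Table 1, at least 16-19 days in block 1 and 1-4 days in block 2, and up to 61 days if the money falls in a sixth weekly instalment and the first is paid a week after discharge.

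The statistical consequence is limited to a possible period effect that the two-factor ANOVA leaves in the error. With the two orders equally represented, the average PHEN-placebo difference is unbiased. The size of the period effect cannot be computed, and the discounting ratios are illustrations under assumed rates. This is a real inconsistency with an inexpensive remedy, not a defect that undermines the trial's main comparison.

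**What to change.** In section 15, take choice earnings out of the post-discharge payment and pay each session's amount, at most $2.50, on the session day after the task. Add the step to Table 3. Leave the daily stipend and completion allowance on the weekly post-discharge schedule. The money option then matches its instruction and has the same delivery time in both blocks.

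If same-day payment is not feasible, change the section 7 instruction so that subjects are told when money is paid. That makes the instruction true but leaves the delay different by block; a period term in the ANOVA could then take up an average shift.

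The cost is a short edit and minor cash handling. The money is 8 x $2.50 = $20 per subject, or 36 x $20 = $720 for 36 completers. It is already inside the $2660 per subject, although the documents give no cash-handling cost. Subjects would hold a little cash that they may be unable to spend on the unit, so part of the practical delay may remain.

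### Sampling-phase peak and AUC are analysed as raw scores with no stated use of each session's pre-cocaine reading, which could sharpen the COC and COC × PHEN comparisons for some secondary measures

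*Combined protocol and SAP*

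**What the plan says.** All references are to section 7, Research Procedures.

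- **Scale.** The Data Analysis paragraph opens with "Data will be analyzed as raw scores".
- **Model.** The progressive-ratio outcomes go into a "two-factor mixed-model ANOVA with COC (within-subject variable; 0 [placebo], 20, 40 and 80 mg), and PHEN" as the second within-subject factor. For the other measures: "Peak-effect and AUC data for the cardiovascular, performance and subjective effects measures obtained during the sampling phase will be analyzed in a similar fashion". No covariate, change score or baseline-corrected AUC is named, and neither peak nor AUC is defined.
- **Pre-dose reading.** The Sampling Phase paragraph schedules the questionnaires and the performance task "30 minutes before the sampling dose of intranasal COC, immediately following and at 15-min intervals for 60 minutes", and adds: "Cardiovascular measures will also be recorded at these times". Table 3 agrees. Its 0900 entry is "Vital signs recorded. Computerized tasks completed. ECG monitoring begins", and COC follows at 0930.
- **Order and timing.** COC doses are given in random order. The maintenance capsule is given at 0700, so the 0900 reading is taken on PHEN or its placebo.
- **Use of the results.** Attenuation is inferred if either the PHEN main effect or the COC × PHEN interaction is significant. Tukey's HSD then uses the ANOVA mean square error.

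**The concern.** The within-subject design removes stable differences between subjects. It does not remove a subject's variation from one session day to the next, such as a higher resting heart rate or a more tired morning. If that variation is already visible at 0900 and carries through to the post-dose values, it inflates the error term for COC, for COC × PHEN and for the post-hoc comparisons.

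The 0900 value precedes that day's randomly ordered COC dose and cannot be affected by it, so it is a legitimate covariate for these effects. What is at stake is precision in secondary answers: attenuation of subjective effects and tolerability of the combination, both hypothesised in section 1.

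**Working it through.** **Inputs from the documents.** 36 subjects; 2 PHEN conditions × 4 COC doses = 8 sessions; a 0900 reading in each; alpha 0.05.

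**Inputs not in the documents (assumed).** *r* is the within-subject, session-level correlation between the 0900 value and the post-dose peak or AUC, taken as 0, 0.3, 0.5 and 0.7. *k* is the ratio of the pre-dose to the post-dose session-level SD, taken as 1 unless stated.

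**The plan's own figure.** None is given for sampling-phase measures. The stated N = 36, d = 0.44 and power 0.80 concern the progressive-ratio outcomes. As a paired t test, N = 36 and d = 0.44 give power 0.73 two-sided and 0.83 one-sided; the plan does not state sidedness. That is a separate matter. The two-sided 0.73 serves below only as a raw-score reference for an illustrative contrast.

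**Formulas, relative to raw-score error variance = 1.**
- Covariate: 1 − r².
- Covariate after losing one df: (1 − r²) × 105/104, because the COC × PHEN error has 35 × 3 = 105 df.
- Equivalent sample-size factor: 1/(1 − r²).
- Change score: 1 + k² − 2rk, which is 2(1 − r) at k = 1.

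| r | Covariate | After df loss | Sample-size factor | Change score | Power, covariate | Power, change score |
|---|---|---|---|---|---|---|
| 0 | 1.00 | 1.01 | 1.00 | 2.00 | 0.72 | 0.44 |
| 0.3 | 0.91 | 0.92 | 1.10 | 1.40 | 0.76 | 0.58 |
| 0.5 | 0.75 | 0.76 | 1.33 | 1.00 | 0.84 | 0.73 |
| 0.7 | 0.51 | 0.51 | 1.96 | 0.60 | 0.95 | 0.91 |

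The covariate breaks even when 1 − r² = 104/105, that is, at r of about 0.1. The change score breaks even only at r = k/2, which is 0.5 with equal SDs.

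**Simulation check.** With 36 subjects and the 2 × 4 conditions, the within-block error mean square with the covariate was about 0.99, 0.91, 0.75 and 0.51 of the raw value at r = 0, 0.3, 0.5 and 0.7.

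**PHEN main effect.** The 0900 reading follows the 0700 capsule, so it can contain a steady PHEN effect. In simulation, a constant PHEN shift of 0.5 SD was estimated as 0.50 on raw scores and 0.00 on change scores. If the 0900 value is instead centred on the subject's own mean within each PHEN block, it sums to zero in every block and is orthogonal to PHEN. The simulated PHEN main effect was then identical with and without the covariate. This identity needs complete sessions.

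**The case against.** **No error is shown.** COC order is random and each subject receives every condition, so the raw-score COC and COC × PHEN contrasts are not biased by leaving out the covariate. This stands. A reader might infer that the planned analysis is invalid or that its error terms are certainly widened. The documents support neither: the gain depends on a correlation they do not give, and near r = 0 there is none.

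**The primary question is untouched.** This stands too. Break point and doses earned have no pre-dose counterpart, and no precision target is set for the sampling-phase measures.

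**The gain is weakest where the subjective hypothesis lies.** The DEQ items in Appendix A ask what the drug is doing now, so pre-dose answers are probably near zero (an assumption). Such items gain nothing. The likely beneficiaries are vital signs, DSST and probably ARS items.

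**The reading may not be wholly unused.** AUC is undefined, so the 0900 point might enter it. One can say only that no use is described.

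**The previous day's COC could affect the 0900 value.** Sessions fall on consecutive days. COC earned at 1430 precedes the next reading by 18.5 hours, and section 9 says side effects usually pass in under 24 hours. The amount earned is also what PHEN is meant to change. The possibility is real and its size unknown. In simulation, a modest carryover did not materially bias the COC × PHEN contrast.

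**Adjustment would split the attenuation rule over two models.** This would hold if adjusted results served the interaction and unadjusted results the PHEN main effect. Block-centring avoids it, because one model gives both.

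**Conclusion.** The point holds as an optional gain in precision for secondary sampling-phase measures. For those with real day-to-day pre-dose variation, the plan as written leaves removable variation in the COC and COC × PHEN error terms. The change in error variance would be about 0%, -9%, -25% or -49% at r = 0, 0.3, 0.5 or 0.7. The PHEN main effect gains nothing and loses nothing.

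This rests on an assumed r, on a common slope across COC and PHEN conditions, and on little carryover from the previous day. The upper end, equivalent to 96% more subjects, needs r = 0.7 after subject effects are removed; nothing in the documents shows that r is so high.

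A reader might also conclude that change from baseline is the remedy. It is not: with equal SDs it widens error when r is below 0.5, and it removes a steady PHEN effect, although the plan uses the PHEN main effect to infer attenuation.

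**What to change.** In the Data Analysis paragraph, for sampling-phase peak and AUC only:

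1. Add the session's 0900 value, centred on the subject's mean within each PHEN block, as a session-level covariate in the COC × PHEN model. Use that one model for both parts of the attenuation rule.
2. State that simple change scores will not be used.
3. Define peak and AUC, including whether the 0900 point enters the AUC. Table 3 also records vital signs at 0930 before dosing, so name 0900 as the covariate time for all measures.
4. Report raw values for tolerability.

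**Cost.** A few sentences and no new data. The model loses one error degree of freedom, and Tukey comparisons are made on adjusted means. The covariate changes from session to session, so the data need one row per session. The progressive-ratio analysis and the sample size stay as they are.
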